4 STUDY DESIGN

4.1 OVERALL DESIGN

The primary study hypothesis is that the time to achieve RTS criteria for pediatric patients with apophysitis of the knee who receive iontophoresis with DSP treatment and PT will be different than those who receive placebo or PT alone. The secondary study hypotheses are: that the patient reported outcomes for pediatric patients with apophysitis of the knee who receive iontophoresis with DSP treatment and PT will be different than those who receive placebo or PT alone; and the frequency and intensity of adverse events among pediatric patients with apophysitis of the knee who receive placebo or PT alone.

This is a Phase II trial. It is a three-arm, randomized, double-blind, placebo-controlled comparison study looking at the functional and patient reported outcomes of iontophoresis (with DSP or placebo) in conjunction with PT versus PT alone to treat pediatric patients diagnosed with apophysitis of the knee.

The study is double-blinded and placebo-controlled to minimize bias. There will be three (3) study groups

- Iontophoresis using DSP (study drug) + PT
- Iontophoresis using placebo + PT
- o PT alone

Participants in all three groups will receive the standard PT protocol for apophysitis of the knee. This will involve up to 20 visits. Participants randomized to the iontophoresis groups will receive up to 12 iontophoresis treatments over a maximum of eight (8) weeks. All participants will receive a phone follow-up call 30 days after they meet RTS criteria as well as an electronic survey follow-up 90 days after they meet RTS criteria.

This study will only be conducted through the Children's Hospital of the King's Daughters Sports Medicine PT Department with study-related activities occurring at six of CHKD's Hampton Roads PT clinics. All study-related activities will be completed by Physical Therapists and Physical Therapist Assistants (Treating Therapists) trained on the protocol and CITI trained.

Concomitant therapies, age, gender, and race will be conducted to analyze the possible effects of these covariates on length of time to RTS

Stratifications of age, gender, and race will be conducted to analyze the possible effect of these covariates on length of time to RTS as well as on patient reported outcomes LEFS, Godin Leisure-Time Activity, and FACES Pain Scale and on safety outcomes.

4.2 SCIENTIFIC RATIONALE FOR STUDY DESIGN

The study is designed to compare the efficacy of iontophoresis with DSP as part of a comprehensive PT treatment. This will be compared to a placebo group receiving iontophoresis with placebo in combination with PT and to a third group receiving PT alone. The use of these control groups is proposed due to the high placebo effect observed in the pediatric population. It is proposed that in groups receiving DSP or placebo to minimize bias. Due to the fact that the third group is receiving only PT, it will be impossible for the subjects or Treating Therapists to be blinded to group assignment.

Because current literature on knee apophysitis treatment typically recommends Non-Steroidal Anti-Inflammatory Drugs (NSAID's), ice, rest, home exercises, bracing, and PT, the placebo group and the PT only group would still be receiving what is cited as appropriate treatment for the diagnosis. Therefore, there should be no ethical concerns with using a control group receiving iontophoresis with placebo or with a group receiving PT alone.

4.3 JUSTIFICATION FOR DOSE

DSP will be supplied as a 4 mg/ml concentration, with 1.5 ml of the solution used for each iontophoresis treatment per the labeling instructions and current standard of practice.

0.9% sodium chloride (placebo) will be supplied at a volume equal to that of the DSP to appear identical for blinding purposes.

4.4 END OF STUDY DEFINITION

A participant is considered to have completed the study if he or she has completed all phases of the study including the last visit or the last scheduled procedure shown in the Schedule of Activities (SoA), Section 1.3. The clinical trial is considered completed when the last participant's last scheduled study-related activity is completed.

5 STUDY POPULATION

5.1 INCLUSION CRITERIA

In order to be eligible to participate in this study, an individual must meet all of the following criteria:

- 1. Written approval from the referring physician for potential subject to be considered for enrollment into this study
- 2. Provision of signed and dated informed consent form
- 3. Stated willingness to comply with all study procedures and availability for the duration of the study
- 4. In good general health as evidenced by written approval from referring physician for potential inclusion in study.

- 5. Has the ability to effectively identify pain/burns and communicate with the investigators or their parents that they are experiencing pain or burning during treatment
- 6. Referred to CHKD Sports Medicine PT by CHKD Primary Care Sports Medicine physicians or CHKD Orthopedics physicians with a diagnosis of apophysitis of the knee and with a prescription for standard PT treatment with iontophoresis
- 7. Able and willing to complete iontophoresis treatments within eight (8) weeks of first treatment
- 8. Must be ambulatory
- Males 7 to 14 years of age who have not reached skeletal maturity (skeletal maturity based on referring physician's clinical judgement or as demonstrated via radiograph images taken within 90 days of enrollment)
- 10. Females 7 to 14 years of age who have not reached skeletal maturity (skeletal maturity based on referring physician's clinical judgement or as demonstrated via radiograph images taken within 90 days of enrollment) and who meet one of the following criteria:
 - a. Pre-menarcheal
 - b. Within two (2) year post onset of menses
- 11. Males or females over the age of 14 only with radiographic evidence of skeletal immaturity, with images taken within 90 days of enrollment
- 12. Index knee symptomatic for pain with activities of daily living or while playing sports.

5.2 EXCLUSION CRITERIA

An individual who meets any of the following criteria will be excluded from participation in this study:

- 1. Index knee symptomatic for pain only with palpation and not with activities of daily living or while playing sport
- 2. Diagnosis of bilateral apophysitis of the knee where both knees meet all of the inclusion criteria
- 3. Systemic fungal infections
- 4. Has an implanted electronic device
- 5. Has a known sensitivity to DSP
- 6. Presence of damaged skin, denuded skin, or other recent scar tissue on index knee
- 7. Presence of active dermatologic conditions in the affected area (e.g., eczema, psoriasis)
- 8. Presence of an abnormal neurological exam that indicates the subject would have a reduced ability to perceive pain (e.g. peripheral neuropathy)
- 9. Has a known sensitivity to electrical current
- 10. Is currently taking systemic steroids
- 11. Has had iontophoresis with DSP treatment within the past 30 days
- 12. Previously enrolled in this study
- 13. Currently enrolled in another treatment research study

5.3 LIFESTYLE CONSIDERATIONS

As part of standard of care, patients will be provided instructions for icing, limiting physical activity, and taking NSAIDs and bracing their knee as recommended by their referring physician. Lifestyle considerations specific to this study, include:

- Adhere to the SoA (see Section 1.1.3 Schedule of Activities)
- Wear their patch for the full two (2) hours, then discard in a trashcan

5.4 SCREEN FAILURES

Screen failures are defined as participants who consent to participate in the clinical trial but are not subsequently randomly assigned to the study intervention or entered in the study. A minimal set of screen failure information is required to ensure transparent reporting of screen failure participants. Minimal information includes demography, screen failure details, eligibility criteria, and any serious adverse event (SAE).

5.5 STRATEGIES FOR RECRUITMENT AND RETENTION

Potential subjects for this study will include patients referred to CHKD Sports Medicine PT by CHKD Primary Care Sports Medicine physicians or CHKD Orthopedic physicians with a diagnosis of apophysitis of the knee and with a prescription for standard PT treatment and iontophoresis. CHKD Primary Care Sports Medicine physicians and CHKD Orthopedic physicians may provide the patient and his/her family an informational flyer about the study and will be encouraged to contact the Principal Investigator if they are interested in learning more about it before their initial PT evaluation.

Given the natural course of apophysitis of the knee, this study population will involve children. All children ages 8 to 17 years old will give both verbal and written Assent as well as their parent/guardian providing written consent for those less than 18 years of age.

Based on the analysis plan, a total of approximately 49 subjects per group will be required, with a total enrollment of 147 subjects.

All potential subjects who are screened to participate in the study will be documented on a Screening Log.

6 STUDY INTERVENTION

6.1 STUDY INTERVENTION(S) ADMINISTRATION

6.1.1 STUDY INTERVENTION DESCRIPTION

The study intervention for this project is DSP administered via iontophoresis. Iontophoresis is a noninvasive delivery mechanism for transmitting a medication to a local area of the body. The I-Bresis[™] System and I-Bresis[™] Patch will be the delivery system utilized for this study. The I-Bresis[™] System is indicated for the administration of soluble salts or other drugs into the body for medical purposes as an alternative to hypodermic injection. The I-Bresis[™] System consists of three components: a Charging Station, a rechargeable Controller and a disposable Patch. The I-Bresis[™] Patch is a disposable, single-use patch with a battery and current-limiting circuitry, and can deliver both negatively and positively charged water-soluble drug/compounds across intact skin. The I-Bresis[™] System will be used in accordance with instructions for use.

- Device size(s) Patch: 13.5cm x 6.5cm that holds 1.5mL of fluid on each side of the patch
- Device model(s)
 - I-Bresis[™] charging station: 1360
 - I-Bresis[™] Controller: 1361
 - I-Bresis[™] Patch: 5000060

- Description of each component
 - The I-Bresis[™] charging station is a rectangular piece of equipment that has four charging ports to which I-Bresis[™] Controller attaches. This device is plugged into a standard wall outlet for power. Each individual charging port has a light to signify if the device is charging (yellow) or fully charged (green).²¹
 - The I-Bresis[™] Controller: 1361 is a small triangular device that attaches to the I-Bresis[™] Patch. There are three buttons on top of the device: Power, Start/pause, and standard mode. There is a light on the front of the device that blinks when the device is powered on. The light is solid when the device is running.²²
 - The I-Bresis[™] Patch is a 13.5cm x6.5cm adhesive patch with two "patch drug pads", each of which are labeled with a polarity of either positive (+) or negative (-). Each drug pad holds ~1.5 ml of fluid. Approximately 1.5 ml of a water-soluble drug/solution is placed on one drug pad and approximately 1.5 ml of the saline solution (supplied in the I-Bresis[™] Patch carton as single-use, sealed vials of sterile 0.9% saline solution) is placed on the other.²³
- Device settings and programming : 3mA current for three (3) minutes then 0.67mA for 120 minutes
- Duration of exposure: 123 minutes (3 minutes of patch + controller, 120 minutes of patch only)
- Frequency of exposure : maximum twice per week for a total of 12 sessions over a maximum of eight (8) weeks

The I-Bresis[™] System is commercially available and will be used in accordance with approved labeling.

The drug and solution administered via the iontophoresis patch will be DSP and 0.9% sodium chloride (placebo).

Dexamethasone sodium phosphate (DSP) is a synthetic adrenocortical steroid that has potent antiinflammatory effects but lacks the sodium-retaining property of hydrocortisone. Corticosteroids inhibit multiple inflammatory cytokines resulting in decreased edema, fibrin deposition, capillary leakage, and migration of inflammatory cells thereby suppressing inflammation. DSP 0.75 mg has anti-inflammatory activity equivalent to approximately 5 mg of prednisone, 25 mg of cortisone, and 20 mg of hydrocortisone. DSP is long-acting (half-life 200 minutes) and is recommended as adjunctive therapy in a variety of inflammatory disorders and as an immunosuppressant agent.¹¹

0.9% Sodium Chloride injection: is a sterile, nonpyrogenic solution of sodium chloride in water for injection. The solution contains 9 grams/L sodium chloride, USP (NaCl), with 154 mEq/L sodium and 154 mEq/L chloride. The nominal pH of sodium chloride is 5.0 (4.5 to 7.0) and osmolarity is 308 mOsmol/L.²⁴

6.1.2 DOSING AND ADMINISTRATION

The I-Bresis patch is designed to hold 1.5mL of fluid on each side (negative and positive) of the patch. DSP is supplied in 120 mg/30 mL (4 mg/1 mL) multidose vials, and will be repackaged into blinded bottles holding 1.8 mL (7.2 mg). 0.9% sodium chloride will be repackaged into blinded bottles holding 1.8 mL. Both DSP and 0.9% sodium chloride will be administered using the I-Bresis System.

6.2 PREPARATION/HANDLING/STORAGE/ACCOUNTABILITY

6.2.1 ACQUISITION AND ACCOUNTABILITY

DSP injection and 0.9% sodium chloride injection will be supplied by the CHKD Pharmacy Department in identical looking single-use bottles, each containing 1.8 mL of solution and labeled in a blinded fashion as either lontophoresis Study Drug "A" or "B". These bottles will be provided by the pharmacy to the outpatient PT clinics and administered by the investigators to the patients. Trained site staff in the PT clinics will be responsible for accountability of the study drug, exercising accepted medical and pharmaceutical practices. Expired or unused study drug bottles will be returned to the CHKD Investigational Pharmacy and disposed of per the CHKD Pharmacy Investigational Drug Policy.

For all study bottles prepared, the CHKD Investigational Pharmacy will keep a compounding log to record the following information: date of preparation, manufacturer, lot number, manufacturer expiration date, number of bottles prepared, expiration date of the study bottles, and assigned numbers of the bottles. This compounding log will only be accessible to study pharmacists to ensure blinding is maintained.

6.2.2 FORMULATION, APPEARANCE, PACKAGING, AND LABELING

DSP Injection, USP 4 mg/mL (Fresenius Kabi USA, LLC) is a clear colorless solution of DSP in water for injection. DSP will be provided in individual empty bottles, each containing 1.8 mL (7.2 mg DSP). Each bottle will contain 1.5 mL (6 mg) DSP for study administration and 0.3 mL of overfill to account for loss during transfer. Each bottle will be labeled identically to the placebo with the label designating assigned bottle number, study drug "A" or "B" and the expiration date clearly marked on the label.

0.9% Sodium Chloride Injection, USP (Baxter Healthcare Corporation) is a clear colorless solution of sodium chloride in water for injection. The 0.9% sodium chloride solution will be provided in individual empty bottles, each containing 1.8 mL (no active drug). Each bottle will contain the 1.5 mL dose to be administered and 0.3 mL overfill to account for loss duringtransfer. Each bottle will be labeled identically to the DSP with the label designating assigned bottle number, study drug "A" or "B" and the expiration date clearly marked on the label.

6.2.3 PRODUCT STORAGE AND STABILITY

All bottles (study drug and placebo) will be stored in a secured space at each of the study sites. These bottles will be stored between 20° to 25°C (68° to 77°F), and will be protected from freezing and excessive heat. All bottles will have a shelf life of 30 days from transfer and the expiration date will be clearly marked on the label. All bottles will be protected from light.

lontophoresis supplies, controlling stations, chargers, and patches will be stored in the outpatient clinics at room temperature per the device labeling instructions.

6.2.4 PREPARATION

DSP and 0.9% sodium chloride will be supplied by the CHKD Pharmacy Department in identical looking bottles, each containing 1.8 mL of solution and labeled in a blinded fashion as either Drug "A" or "B". Trained Therapists will be responsible for the preparation of the iontophoresis patches. Aseptic techniques will be utilized when preparing the patches. Upon randomizing a subject, the treating physical therapist will retrieve the appropriately labeled bottle ("A" or "B", based on the subject's randomization assignment) from the locked cabinet and check the expiration date. The treating physical therapist will apply 1.5 mL liquid (from the assigned bottle) to the negative side of the patch per the instructions listed in the I-Bresis Instruction for Use. The Therapist will then apply 1.5mL of 0.9% sodium chloride from the saline ampoules provided in the I-Bresis[™] carton to the positive side of the patch and will then obtain two patient identifiers (ex. Full name, DOB) from the patient prior to patch application per clinic policy.

The treatment site will be cleaned thoroughly with alcohol prep (ensuring the area being treated is free from other creams and topical medications, including topical steroids) as described in the instructions listed in the I-Bresis Instructions for Use.²³ The negative side of the patch will be applied over the tibial tubercle in patients with OSD and over the inferior patellar pole in patients with SLJ.

The I-Bresis controller will be turned on then connected to the patch. At that time, the start button will be pressed and the current will be initiated at 3mA for an initial 3minutes of treatment. Following this three minutes, the controller will be removed and turned off. The Patch will remain in place and an 80 mA-minute dose will be applied over two hours. The therapist will ensure that the patch fully conforms to the patient and that it will maintain full contact with the skin. To improve adhesion of the patch, the therapist may lightly wrap the patch with Pre-Wrap and secure the end with tape, ensuring the tape is not being applied over the patch so as not to bind it.

Subjects will be monitored by their therapist for adverse events for 15 minutes after the patch is applied following the initial application and for an appropriate amount of time following all subsequent applications. Subjects will leave the PT clinic with the patch in place. The patch will be programed to deliver medication over a two-hour period, automatically switching off iontophoresis after the maximum dose has been administered. Subjects will be instructed to remove the patch 2 hours after it has been applied as leaving the patch on longer than the recommended time may increase the risk of skin irritation. Subjects will be instructed to wrap the patch in paper towels and discard the Patch in a receptacle out of reach of children and pets.

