6.3 MEASURES TO MINIMIZE BIAS: RANDOMIZATION AND BLINDING

A center-stratified randomization method will be used to maintain balance between treatment groups and centers. Equal number of participants per intervention will be considered to maximize study power. The CHKD Pharmacy Department will hold the randomization key and will prepare bottles of study drug and placebo (see Section 6.2.2 Formulation, Appearance, Packaging, and Labeling).

Treating therapists will assign randomization codes in chronological order as participants enroll in the study. Since the study drug and sodium chloride are identical in appearance, the Treating Therapists will

be blinded to study assignment. Those participants assigned to "Group C", or standard PT alone, will be unblinded to treatment as they will not receive iontophoresis.

In the case of an unexpected and serious adverse event in which knowing the study assignment is critical to the medical care of the participant, the CHKD pharmacist may release this information to the Independent Safety Monitor only, who may share this information with the treating physician.

Both the Treating Therapist and the participants assigned to one of the two iontophoresis groups will be blinded to study treatment. The DSP injection and 0.9% sodium chloride injection are clear, colorless liquids that will be supplied by the CHKD Pharmacy Department in identical looking single-use bottles. Each bottle will contain 1.8 mL of solution and will be labeled in a blinded fashion as either lontophoresis Study Drug "A" or "B".

In this study, the Treating Therapists will also perform all physical therapy assessments. While having a separate group of "assessing therapists" and "treating therapists" minimizes bias even further than the current study design, combining their roles is preferred as it reduces error by minimizing the number of therapists involved, improves completion consistency of the RTS Criteria Checklist, and minimizes scheduling conflicts caused when trying to coordinate two therapist's schedules for every study visit conducted.

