- FACES Pain Scale (see Appendix 12.2) a patient reported paper-based questionnaire that asks the patient to choose the face that best represents the pain they are experiencing in their knee. Assessed at the end of each Study Treatment Visit and again at the end of the Clinic Check Visit.
- RTS Criteria Checklist (see Appendix 12.3) a paper-based checklist completed by the Treating
 Therapist to determine whether or not the participant is ready to safely return to sport. The
 checklist was created to include the basic movements typically required for sports activities,
 though these activities are also applicable for return to PE participation and free play, making it
 appropriate for all patients, even those not involved in organized sports. These movements
 include squatting, running, bilateral and unilateral jumping, back pedaling, and quick direction
 changes. The checklist includes qualifying criteria for proper mechanics and requires that all
 activities be pain-free. The checklist was created to assess readiness for sports participation
 without actually requiring that the patient return to sport participation to meet criteria, as not
 all patients participate in organized sports or are in-season year round. The items assessed as
 part of this checklist are all part of normal standard of care for physical therapy. Assessed at
 each Study Treatment Visit and again at the Clinic Check Visit.
- Godin Leisure-Time Exercise Questionnaire (see Appendix 12.4) a paper-based subject self-reporting questionnaire comprised of four (4) items that address the amount of time an individual engages in mild, moderate, and strenuous leisure time physical activity of at least 15 minutes in duration during a typical week. Assessed at Study Treatment Visit 1 and at the 30-day phone follow-up (see Appendix 12.5 30-Day Phone Follow Up) and 90-Day Follow-Up (see appendix 12.6 90-Day Follow-Up Electronic Survey).
- Study Treatment:
 - Iontophoresis (Groups A and B only) ~ 3 minutes in clinic and 2 hours at home The iontophoresis patch will be applied by a trained therapist in blinded fashion for all participants assigned to groups A and B (see section 6.1.2 Dosing and Administration). Performed at Study Treatment Visits 1 12 (Maximum of 12 treatments, maximum of 8 weeks since first Study Treatment Visit, or when RTS criteria are met and confirmed at the Clinic Visit Check, whichever is sooner).

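### Two fixed bottle letters, which are also the arm names, tie the blind of all 98 iontophoresis participants to one piece of knowledge, and the therapists who handle the letters score the primary endpoint

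*Combined protocol and SAP*

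**What the plan says.** Section 6.2.4 describes bottles that look the same, "each containing 1.8 mL of solution and labeled in a blinded fashion as either" Drug A or Drug B. The therapist retrieves the bottle by its letter, "based on the subject's randomization assignment". Sections 6.2.1 and 6.3 repeat the two-letter labelling.

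Section 6.2.2 says of the DSP bottles: "Each bottle will be labeled identically to the placebo with the label designating assigned bottle number", followed by the letter and the expiry date. A bottle number therefore exists, but the letter is printed with it.

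The letters are also the arm names. Section 8.1 lists "Iontophoresis (Groups A and B only" as the study treatment, and Section 6.3 says that those in Group C "will be unblinded to treatment as they will not receive iontophoresis".

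On outcome assessment, Section 6.3 states that "the Treating Therapists will also perform all physical therapy assessments". Under Section 8.1 this includes the RTS checklist, which defines the primary endpoint.

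On emergency unblinding, Section 6.3 says that "the CHKD pharmacist may release this information to the Independent Safety Monitor only, who may share this information with the treating physician". The pharmacy holds the randomisation key (Section 6.3), and only study pharmacists can see the compounding log (Section 6.2.1).

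**The concern.** With one letter per solution throughout the trial, the blind is a single shared fact. It is not a separate fact for each participant. Knowing what A means gives B by elimination, for every past and future child in those two arms.

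This matters more here than in most trials, for three reasons.

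- DSP against placebo iontophoresis is the only blinded comparison.
- The plan chooses not to use separate assessors, so the bottle code is the main protection for the primary endpoint. Parts of the RTS checklist (Section 12.3) call for judgement, such as movement quality, softness of landing and effort.
- Section 2.3.3 records a strong prior belief among the investigators that DSP iontophoresis speeds recovery. Staff who share it may read whichever letter seems faster as the active one.

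Therapists see pain ratings, the knee examination and the checklist at every study treatment visit, up to 12 per child. Shared letters let those impressions add up across children; separate codes would limit this.

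**Working it through.** **1. The plan's own figures.** Section 9.2 gives f = 0.28, 80% power and alpha 0.05. A three-group one-way F test (noncentrality N x f^2, degrees of freedom 2 and N - 3) first reaches 80% power at N = 126 (power 0.8002), as stated. Then 126 x 1.15 = 144.9, which rounds up to 147 for three equal groups of 49. The point below needs only the 49 per group.

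**2. Does each letter mean one solution throughout the trial?** The protocol does not say so in one sentence, but it follows from three statements. The bottles carry A or B (6.2.1, 6.2.2, 6.2.4, 6.3). The bottle is chosen by letter from the randomised arm (6.2.4). The arms are called Groups A and B in every clinic (1.3, 6.4, 8.1). No section describes further codes, letters that vary by clinic, or participant-level codes.

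**3. Exposure if one code's meaning is learned.**

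- Two letters, as planned: 2 x 49 = 98 of 98 blinded participants, or 98/147 = 67% of the trial. The other 49 are already open.
- Three codes per solution: 98/6 = 16.3, so about 16 known with certainty.
- Participant-level codes: 1.

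**4. How likely is a formal break?** Section 6.3 limits release to unexpected, serious events where the assignment is critical to care. Section 2.3.3 reports over 23,000 DSP iontophoresis treatments with no significant adverse reaction. The rule of three gives an upper limit of about 3/23,000 per treatment. With at most 49 x 12 = 588 DSP applications, 588 x 3/23,000 = 0.08 expected events. Applying the same rate to both iontophoresis arms gives 1,176 x 3/23,000 = 0.15. This is rough: clinic experience is not trial surveillance, and a significant reaction is not the same criterion as the one for release.

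**5. How could impressions accumulate by letter?** The documents give no rate for any cue that differs between DSP and placebo, so the rates below are assumptions. Suppose a cue appears in a proportion p1 of DSP children and p0 of placebo children.

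- Guessing one child at a time is right with probability 0.5 x (p1 + 1 - p0).
- Comparing two codes with m children each, and calling the one with more cues DSP, is right with probability P(X > Y) + 0.5 x P(X = Y), where X is binomial(m, p1) and Y is binomial(m, p0).

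The values of m assume equal enrolment at the six clinics: 98/(2 x 6) = 8.2 per letter per clinic now, and 98/(6 x 6) = 2.7 per code per clinic with three codes per solution, taken as 3. The value 49 is the whole trial.

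| Assumed p1 v p0 | One child | m = 3 | m = 8 | m = 49 |
|---|---|---|---|---|
| 0.20 v 0.10 | 0.55 | 0.62 | 0.71 | 0.92 |
| 0.40 v 0.20 | 0.60 | 0.70 | 0.81 | 0.99 |
| 0.30 v 0.10 | 0.60 | 0.71 | 0.84 | 0.99 |

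Pooling by letter turns a weak cue into a better guess. One therapist may see fewer than 8 children per letter, and none would see 49, so the m = 8 column is the more relevant and may still be too high.

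**The case against.** A reader might infer that a single emergency code break unblinds the whole trial and biases all later RTS scores. The documents do not support this. Group C has no blind to lose. The release route in Section 6.3 runs from the pharmacist to the safety monitor and possibly the treating physician, and the therapists who score RTS are not on it. A further leak would be needed, and on the investigators' own experience a release looks rare. This part of the objection stands.

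The inference route can also be challenged. Section 2.3.1.1 lists skin effects under iontophoresis itself, which both blinded arms receive; of the causes it gives for the rarer skin reactions, only sensitivity to the solution would obviously differ by arm. Quick relief is a weak cue in a self-limited condition where everyone receives physical therapy. No section reports a DSP-placebo difference in anything visible. This also stands: the table above shows a mechanism and does not estimate how often therapists would guess right.

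Nor do therapists choose letters freely. They assign codes in chronological order and retrieve the matching bottle.

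The restricted log and the pharmacy-held key are real safeguards. They protect the key from being read, but not from being inferred. Section 6.3 acknowledges the assessor trade-off openly, but that does not address the shared letters.

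**Conclusion.** The concern holds in limited form. Under the plan as written, learning or inferring one letter's meaning reveals all 98 blinded participants. That count rests on 49 per group and on reading the letters as fixed arm names, which the text supports.

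The main threat to RTS scoring is therapists forming a view of the letters over successive children; the formal break is secondary. Neither the size of any resulting bias nor its probability can be derived from the documents. This is an inexpensive improvement to the protection of the only blinded comparison, and it does not show that the blind will fail.

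**What to change.** In Sections 6.2.2, 6.2.4 and 6.3 (and 6.2.1, to match), have the pharmacy assign several codes to each solution, for example three each. Allocate them at random, hold them in the randomisation key, and show the code rather than the arm on the site randomisation log. The code is then no longer the arm name. One break exposes about 16 participants instead of 98, and each clinic sees about 3 children per code instead of about 8. Some information would still leak: once one of six codes is known, two of the other five hold the same solution and three the other.

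The cost is relabelling, six codes stocked at each clinic instead of two, and some wastage within the 30-day shelf life (Section 6.2.3). Sample size, endpoint and treatment do not change. If enrolment is under way, apply the codes to new participants and report the two-letter period as a limitation.

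Participant-level numbering would limit a break to one participant, but it is optional because it is not a simple swap. The existing number identifies a single-use bottle, and a child may need up to 12. Consent, randomisation and first treatment may fall on one day. The shelf life is shorter than the 8-week course. It would need a bottle-to-participant allocation list and repeated resupply to six clinics.
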